7. INTERIM ANALYSIS

No formal interim analysis is planned.

A first-step analysis may be performed when the last patient completes day 8 of the treatment period and has undergone the Cat Allergen Challenge in the EEU at day 8. No changes in the conduct of the study will be made based on this first-step analysis. The purpose of the first-step analysis is to accelerate the planning of future studies. This will be the final analysis of the primary endpoint of the study. If a decision is made to perform the first-step analysis, in order to maintain study integrity with respect to the treatment follow-up visits, safety visits, and analyses, a dissemination plan will be written. This plan will clearly identify the team (including the statistician) that will perform the first-step analysis and all related activities, restrict other clinical team members and other Sponsor personnel from access to individual patient treatment allocation, and ensure that the dedicated team will not participate in the data review or data decisions for the following treatment analyses. However, the dedicated team can participate in the analysis following the final database lock.

8. SOFTWARE

All analyses will be done using SAS Version 9.4 or above.

10. APPENDIX

10.1. Summary of Statistical Analyses

Efficacy Analysis:

Endpoint	Analysis Populations	Primary Analysis	Statistical Method	Supportive Analysis	Subgroup Analysis	Other Analyses
Primary Endpoint						
Time to EAR	FAS, PPS	Time to EAR (a 20 % drop in FEV1 or when the subject exits the EEU on day 8 due to clinically significant symptoms), censored at 4 hours if the patient does not experience an EAR	Cox proportional hazards model	Yes Kaplan Meier estimates and plots	No	Sensitivity Analysis: Fisher's exact test comparing the proportion of subjects with EAR
Secondary Endpoints						
Time to EAR	FAS, PPS	Time to EAR (a 20 % drop in FEV1 or when the subject exits the EEU on days 29, 57, and 85 due to clinically significant symptoms), censored at 4 hours if the patient does not experience an EAR	Cox proportional hazards model	Yes Kaplan Meier estimates and plots	No	Sensitivity Analysis: Fisher's exact test comparing the proportion of subjects with EAR
AUC of FEV1	FAS	Percent change in the AUC of FEV1 from baseline to days 8, 29, 57, and 85	MMRM	No	No	No
AUC of TNSS	FAS	Change in the AUC of TNSS from baseline to days 8, 29, 57, and 85	MMRM	No	Yes	No

Endpoint	Analysis Populations	Primary Analysis	Statistical Method	Supportive Analysis	Subgroup Analysis	Other Analyses
AUC of TOSS	FAS	Change in the AUC of TOSS from baseline to days 8, 29, 57, and 85	MMRM	No	Yes	No
Cat allergen quantity	FAS	Change and percent change in cat allergen quantity as experienced by patients from baseline to days 8, 29, 57 and 85	MMRM	No	No	No

Safety Analyses:

Endpoint	Analysis Populations	Primary Analysis	Statistical Method	Supportive Analysis	Subgroup Analysis	Other Analyses
Adverse Events	FAS	Percent of patients by system organ class	Descriptive Statistics	No	No	No

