## **10.3. Analysis Sets**

### **10.3.1. Efficacy Analysis Sets**

The FAS includes all randomized patients who received any study drug; it is based on the treatment allocated (as randomized). Efficacy endpoints will be analyzed using the FAS.

The per protocol analysis set (PPS) includes all patients in the FAS except for those who are excluded because of efficacy-related major protocol violations. Final determination of the PPS will be made prior to the database lock and will be outlined in the SAP.

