#### **10.4.4. Safety Analysis**

Safety analysis will be based on the SAF. This includes reported TEAEs and other safety data (ie, clinical laboratory evaluations and vital sign results). A descriptive summary of safety results will be presented by treatment group.

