3.1. The Full Analysis Set (FAS)

FAS includes all randomized subjects who receive any investigational product and have completed the Day 8 Cat Allergen Challenge. Efficacy analyses will be based on the treatment allocated by the IVRS at randomization (as randomized).

FAS is the primary analysis set for efficacy endpoints.

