3.3. The Safety Analysis Set (SAF)

SAF includes all subjects who receive any investigational product and be analyzed as treated. Treatment compliance/administration and all clinical safety variables will be analyzed using the SAF. No missing data will be imputed for safety analyses.

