5.7. Analysis of Safety Data

The analysis of safety and tolerance will be performed on the SAF, as defined in Section 3.3.

The safety analysis will be based on the reported AEs and other safety information (clinical laboratory evaluations, vital signs and 12-lead ECG).

Thresholds for Potential Clinically Significant Values (PCSV) in laboratory variables, vital signs and ECG are defined in Section 10.3.

The summary of safety results will be presented for each treatment group.

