5.7.1. Adverse Events

The verbatim text, the PT, and the primary SOC will be listed in subject listings. Summaries that include frequencies and proportions of patients reporting AEs will include the PTs and the SOCs.

AEs will also be summarized by relationship to EEU procedure. Also, asthma related AEs, specifically, reported throughout the study will be presented for each treatment group and will be summarized by relationship to EEU procedure. Medications used to treat any asthma related AEs will also be listed and summarized by treatment group.

Period of observation: The observation period will be divided into two segments: pre-treatment and treatment periods. The pre-treatment period is defined as the time between when the subjects

give informed consent to before the single dose of study drug. The on-treatment period is defined as the time after the single dose of study drug until the end of study (week 16).

Day 1 is the first day of investigational product, Day -1 is the day before, and there is no Day 0.

Pre-treatment AEs are defined as AEs that developed or worsened during the pre-treatment period.

Treatment-emergent AEs (TEAEs) are defined as AEs that developed or worsened during the treatment period.

The focus of adverse event reporting in the clinical study report will be on TEAEs.

For details on handling missing data and partial dates, see Section [6](#).

Summaries of all TEAEs in each treatment group will include:

- All TEAEs by system organ class
- Possibly related TEAEs by system organ class
- Possibly related TEAEs by intensity and SOC (recommended)
- Time to first occurrence of any (or selected) TEAE (optional)
- Alert terms: all and possibly related TEAEs (optional)
- Serious adverse events: All and possibly related TEAEs by seriousness criterion
- Serious adverse events: All and possibly related TEAEs by SOC
- Death: All and possibly related TEAEs by SOC
- Other significant adverse events: All and possibly related TEAEs by “other significant” adverse event criterion
- Discontinuation: All and possibly related TEAEs by system organ class
- Non-serious possibly related TEAEs by SOC (mandatory if study includes a German center)

Counts will be provided according to treatment group for each PT within each SOC. Percentages will be calculated using the number of patients from the safety population in each treatment group.

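### SAP Appendix 10.1 names the FAS as the population for adverse events, contradicting the SAF specified in SAP 3.3, 5.7 and 5.7.1 and in the protocol

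*SAP*

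**What the plan says.** Appendix 10.1 of the SAP tabulates each endpoint with its analysis population. Under Safety Analyses there is a single row, Adverse Events. The analysis is given as "Percent of patients by system organ class", the method is descriptive, and the population is the FAS.

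The body of the SAP names a different population:

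- Section 3.3: "Treatment compliance/administration and all clinical safety variables will be analyzed using the SAF".
- Section 5.7: "The analysis of safety and tolerance will be performed on the SAF, as defined in Section 3.3".
- Section 5.7.1, on the AE tables themselves: "Percentages will be calculated using the number of patients from the safety population in each treatment group".

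The protocol agrees with the body of the SAP, in 10.3.2 and again in 10.4.4: "Safety analysis will be based on the SAF".

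The two sets are defined in SAP 3.1 ("FAS includes all randomized subjects who receive any investigational product and have completed the Day 8 Cat Allergen Challenge", with efficacy analysed by allocated treatment) and SAP 3.3 ("SAF includes all subjects who receive any investigational product and be analyzed as treated"). Protocol 10.3.1 defines the FAS without any Day 8 condition: "The FAS includes all randomized patients who received any study drug; it is based on the treatment allocated (as randomized".

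**The concern.** The incidence of TEAEs and serious TEAEs through the end of the study is a listed secondary endpoint (Protocol 4.2, SAP 4.5.2). A table of that incidence should cover everyone exposed. The SAP's FAS does not, because membership depends on something that happens after the dose: completing the Day 8 challenge. A patient dosed on Day 1 who withdraws in the first week, for whatever reason, is outside it.

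The loss would not be confined to the first week. Protocol 7.3.2 asks patients who opt out of the EEU challenges, but do not withdraw, to attend all their remaining visits apart from the EEU exposures and related procedures. A patient who opted out before Day 8 would be followed to week 16, and every adverse event over that time would be absent from a FAS table.

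There is also a difference in arm assignment. The FAS is as randomised and the SAF as treated, so a patient who received the wrong treatment would be counted under a treatment not received.

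An endpoint-by-endpoint summary is a natural source for output specifications, and the SAP gives no rule for resolving a conflict between its body and its appendix.

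**Working it through.** No stated figure is in dispute, so the check is a comparison of texts followed by the denominator arithmetic.

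**Step 1. Population named for adverse events.**

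| Place | Population |
|---|---|
| SAP Appendix 10.1, Adverse Events row | FAS |
| SAP 3.3 | SAF |
| SAP 5.7 | SAF |
| SAP 5.7.1 (denominator of AE percentages) | Safety population |
| Protocol 10.3.2 | SAF |
| Protocol 10.4.4 | SAF |

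Five places agree and the appendix row stands alone. The row is current text and legible, so it is neither superseded wording nor an extraction fault.

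**Step 2. How the sets differ.** Under the protocol, both sets contain all randomised patients who were dosed, and they differ only in as-randomised against as-treated assignment. Under the SAP, the FAS carries the extra Day 8 condition. Let k be the number of dosed, randomised patients who do not complete Day 8. Then

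FAS = SAF − k.

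**Step 3. Size of the omission.** The documents do not give k, and they do not define what counts as completing the challenge. SAP 2.2 plans 30 patients per arm, 60 in all, and allows for 8 dropouts (13%) in the power calculation. Take all 60 as dosed and, as an assumption, let k run from 0 to 8:

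| k | FAS | Share of dosed patients omitted |
|---|---|---|
| 0 | 60 | 0% |
| 1 | 59 | 1/60 = 1.7% |
| 4 | 56 | 4/60 = 6.7% |
| 8 | 52 | 8/60 = 13.3% |

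**Step 4. Direction of any bias.** In one arm of n dosed patients, let a be the number with an AE among those retained and b the number with an AE among the k omitted. The SAF rate is (a + b)/n and the FAS rate is a/(n − k). The FAS rate is lower only when b/k exceeds a/(n − k), that is, when the omitted patients have AEs more often than the retained ones.

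With counts assumed purely for illustration, n = 30, a = 3 and k = 2:

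- Both omitted patients have an AE (b = 2): SAF 5/30 = 16.7%, FAS 3/28 = 10.7%. The FAS understates.
- Neither has an AE (b = 0): SAF 3/30 = 10.0%, FAS 3/28 = 10.7%. The FAS slightly overstates.

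The direction therefore depends on who is omitted, and the documents do not settle that.

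**The case against.** The best case on the other side is that the body of the SAP already settles the matter. SAP 5.7.1 fixes the denominator for exactly the kind of percentage in the disputed row, and SAP 3.3, SAP 5.7 and the protocol agree with it. One cell in an appendix summary is more plausibly a table slip than a chosen analysis. This stands as a reading of intent. It does not make the row correct, because no order of precedence is stated.

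A reader might infer that early events would be hidden. The documents do not support that. It would require the cell to be followed over the body text, a dosed patient to miss Day 8, and that patient to have an AE. Even then, SAP 5.7.1 provides separate summaries for serious events, deaths and discontinuations and puts AEs in subject listings, and Protocol 10.4.4.1 adds listings of deaths and other SAEs.

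A reader might also infer that first-week leavers are the patients most likely to have injection-related or hypersensitivity events, so that incidence must be biased downward. No figure in either document supports this. Day 8 can be missed for other reasons: Protocol 5.1 stops a challenge from going ahead on symptom-score or FEV1 grounds, and patients may opt out. A patient with an injection reaction who completes Day 8 remains in the FAS.

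Finally, the omission comes from the SAP's Day 8 condition. Under the protocol's FAS the row would drop no randomised, dosed patient. That is true, but the SAP's definition is the one the appendix relies on, and the as-randomised against as-treated difference would remain under either definition.

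**Conclusion.** The row is wrong as written. It contradicts SAP 3.3, 5.7 and 5.7.1 and Protocol 10.3.2 and 10.4.4. If followed, it would condition a listed secondary endpoint on a post-dose event and assign any wrongly dosed patient to the randomised arm.

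The size of the effect is unknown. The range of 0% to 13.3% rests on three assumptions: that all 60 planned patients are dosed, that k does not exceed the 8 planned dropouts, and, for the upper end, that all 8 were dosed and lost before Day 8. The 8 is an allowance in the power calculation, which does not say whether or when those patients were dosed. Patients never dosed belong to neither set, so 13.3% should not be read as an expected loss.

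The finding is an internal inconsistency, most likely a drafting slip, and not evidence that the sponsor chose to analyse safety on a reduced set. It still needs correcting, because the intended population is clear and the text in force disagrees with it.

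**What to change.** In SAP Appendix 10.1, change the analysis population of the Adverse Events row from FAS to SAF.

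This alters one table cell. It leaves the efficacy analyses, the sample size and the conduct of the trial untouched, and there is no statistical cost. With the change, the AE denominator is all dosed patients (60, or 30 per arm, if all planned patients are dosed and receive their allocated treatment). Reconciling the SAP's FAS definition with the protocol's would not replace this correction, since the FAS would still be analysed as randomised.

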10.2. Schedule of Time and Events

Table 1: Schedule of Time and Events

Study Procedure	Screening ¹				Randomization and Treatment Period										End of Study/Early Termination Visit	Unscheduled Visit ²⁴
	Visit	V1 ²⁵	Placebo EEU V2 ²⁵	Cat EEU _{3,22} V3	V4	R ² V5	Cat EEU ^{22, 23} V6	Tel ·	Cat EEU ²² V7	V8	Cat EEU ²² V9	Tel ·	Cat EEU ²² V10	V11	V12	
Days		-85 to -14				1	8	9	29	30	57	58	85	86	113	
Window (day)		+7				±3	±2		±2		±3		±3		±3	
Weeks		-12				1	1	2	4	4	8	8	12	12	16	
Screening/Baseline																
Inclusion/Exclusion	X	X	X		X											
Informed Consent	X															
Medical History	X															
Height	X															
Weight	X															
Demographics	X															
HIV screening	X															
Hepatitis screening	X															
Screening Skin prick test for cat allergen ⁴	X															
Skin prick test for other common allergens ⁴	X															
Placebo challenge		X														

Study Procedure	Screening ¹					Randomization and Treatment Period									End of Study/Early Termination Visit	Unscheduled Visit ²⁴
	V1 ²⁵	Placebo EEU V2 ²⁵	Cat EEU _{3,22} V3	V4	R ² V5	Cat EEU ^{22, 23} V6	Tel .	Cat EEU ²² V7	V8	Cat EEU ²² V9	Tel .	Cat EEU ²² V10	V11	V12		
Visit	V1 ²⁵	Placebo EEU V2 ²⁵	Cat EEU _{3,22} V3	V4	R ² V5	Cat EEU ^{22, 23} V6	Tel .	Cat EEU ²² V7	V8	Cat EEU ²² V9	Tel .	Cat EEU ²² V10	V11	V12		
Days	-85 to -14				1	8	9	29	30	57	58	85	86	113		
Window (day)	+7				±3	±2		±2		±3		±3		±3		
Weeks	-12				1	1	2	4	4	8	8	12	12	16		
Screening Cat Allergen Challenge ³			X													
Spirometry ⁵ (includes FEV1)	X	X	X	X	X											
Minute ventilation	X															
Treatment																
Randomization ²					X											
Administer Study Drug ²						X										
Cat Allergen Challenge ³						X		X		X		X				
Concomitant Medications	X	X	X	X	X	X	X	X	X	X	X	X	X	X	X	
Efficacy																
TNSS nasal symptoms score ⁶			X	X		X		X	X	X		X	X	X		
TOSS ocular symptoms score ⁶			X	X		X		X	X	X		X	X	X		
Chest symptoms questions ⁶			X	X		X		X	X	X		X	X	X		
Spirometry (includes FEV1) ⁵						X		X	X	X		X	X	X		
PNIF ⁷			X			X		X		X		X				

Study Procedure	Screening ¹					Randomization and Treatment Period								End of Study/Early Termination Visit	Unscheduled Visit ²⁴	
	V1 ²⁵	Placebo EEU V2 ²⁵	Cat EEU _{3,22} V3	V4	R ² V5	Cat EEU ^{22, 23} V6	Tel .	Cat EEU ²² V7	V8	Cat EEU ²² V9	Tel .	Cat EEU ²² V10	V11	V12		
Visit	V1 ²⁵	Placebo EEU V2 ²⁵	Cat EEU _{3,22} V3	V4	R ² V5	Cat EEU ^{22, 23} V6	Tel .	Cat EEU ²² V7	V8	Cat EEU ²² V9	Tel .	Cat EEU ²² V10	V11	V12		
Days	-85 to -14				1	8	9	29	30	57	58	85	86	113		
Window (day)	+7				±3	±2		±2		±3		±3		±3		
Weeks	-12				1	1	2	4	4	8	8	12	12	16		
Skin Prick Test with Serial Allergen Titration (Cat-SPT) ⁸			X					X				X		X	X	
FeNO ⁹		X		X					X				X			
Safety¹⁰																
Vital Signs	X	X ¹²	X ¹²	X	X ¹ ₁	X ¹²		X ¹²	X	X ¹²		X	X	X	X	
Physical Examination	X		X ²⁷		X	X ²⁷		X ²⁷		X ²⁷		X ²⁷		X	X	
Electrocardiogram	X															
ACT	X	X	X											X	X	
Adverse Events	X	X	X	X	X	X	X	X	X	X	X	X	X	X	X	
Observation			X ²⁰		X ²¹	X ²⁰		X ²⁰		X ²⁰		X ²⁰				
Distribution of rescue treatment kit			X			X		X		X		X				
Telephone Call ¹³						X				X						
Laboratory Testing¹⁴																
Hematology	X				X ¹⁵			X		X		X		X	X	
Blood Chemistry	X				X ¹⁵			X		X		X		X	X	
Urinalysis	X				X			X		X		X		X	X	
βHCG serum pregnancy test	X														X	

Study Procedure	Screening ¹					Randomization and Treatment Period									End of Study/Early Termination Visit	Unscheduled Visit ²⁴
	V1 ²⁵	Placebo EEU V2 ²⁵	Cat EEU _{3,22} V3	V4	R ² V5	Cat EEU ^{22, 23} V6	Tel .	Cat EEU ²² V7	V8	Cat EEU ²² V9	Tel .	Cat EEU ²² V10	V11	V12		
Visit	V1 ²⁵	Placebo EEU V2 ²⁵	Cat EEU _{3,22} V3	V4	R ² V5	Cat EEU ^{22, 23} V6	Tel .	Cat EEU ²² V7	V8	Cat EEU ²² V9	Tel .	Cat EEU ²² V10	V11	V12		
Days	-85 to -14				1	8	9	29	30	57	58	85	86	113		
Window (day)	+7				±3	±2		±2		±3		±3		±3		
Weeks	-12				1	1	2	4	4	8	8	12	12	16		
Urine pregnancy test (for female patients only) ¹⁶		X	X		X ¹⁶	X		X		X		X		X	X	
FSH test (in postmenopausal women only) ²⁸	X															
Serum for specific IgE for Fel d 1 and cat allergen	X		X		X	X		X		X		X				
Serum for sIgE (Fel-D 2, 4, 7) tests ¹⁷			X		X	X		X		X		X				
Research samples (serum and plasma)			X		X	X		X		X		X		X	X	
Research Samples: whole blood for PBMCs					X	X		X		X		X		X	X	
Nasal brushing samples for RNA analysis ²⁶			X					X								
Genomic DNA sample ¹⁸					X											
PK¹⁹ and ADA																

Study Procedure	Screening ¹					Randomization and Treatment Period									End of Study/Early Termination Visit	Unscheduled Visit ²⁴
	V1 ²⁵	Placebo EEU V2 ²⁵	Cat EEU _{3,22} V3	V4	R ² V5	Cat EEU ^{22, 23} V6	Tel .	Cat EEU ²² V7	V8	Cat EEU ²² V9	Tel .	Cat EEU ²² V10	V11	V12		
Visit	V1 ²⁵	Placebo EEU V2 ²⁵	Cat EEU _{3,22} V3	V4	R ² V5	Cat EEU ^{22, 23} V6	Tel .	Cat EEU ²² V7	V8	Cat EEU ²² V9	Tel .	Cat EEU ²² V10	V11	V12		
Days	-85 to -14				1	8	9	29	30	57	58	85	86	113		
Window (day)	+7				±3	±2		±2		±3		±3		±3		
Weeks	-12				1	1	2	4	4	8	8	12	12	16		
Drug conc. sample					X ¹⁵	X ¹⁹		X		X		X		X		X
ADA sample					X ¹⁵							X		X		X

10.2.1. Footnotes for the Schedule of Events Table

1. All screening-related procedure should be performed between day -85 to -14
2. Randomization/study drug administration (visit 5) must occur within 14 to 28 days of visit 3.
3. Controlled Cat Allergen Challenge is performed as described in the study manual.
4. Screening Skin prick test for cat allergen and skin prick testing for other common allergens is performed as described in the study manual. If screening skin prick test for cat allergen is negative at screening visit 1 (mean wheal diameter less than at least 5 mm greater than a negative control), then other screening visit 1 procedures do not need to be performed as the patient will have failed screening based upon cat allergen skin prick testing (eg, perform skin prick testing prior to other allergen skin prick testing, blood draw, spirometry, etc).
5. At screening visit 1, a spirometry session will be completed to check for FEV1 inclusion criteria. At visit 2, spirometry will be performed at baseline prior to the placebo EEU challenge, and then every 10 minutes during the placebo challenge, then every 30 minutes in the supervision room for 6 hours. On the Cat Allergen Challenge visits (3, 6, 7, 9, and 10) spirometry will be performed at baseline prior to entry into the EEU, every 10 minutes during the EEU exposure, every 30 minutes in the observation room for 6 hours after leaving the EEU, and then every hour for up to 18 hours after leaving the clinical unit except during sleeping. At visit 5, on the day of randomization, a spirometry session will be performed twice: once prior to receiving the study drug and once prior to leaving the clinical trial unit. Additional spirometry may be performed when prompted by asthma symptoms.

6. TNSS, TOSS, and chest symptom questions are assessed prior to Cat Allergen Challenge, approximately every 20 minutes during the challenge in the exposure unit, every 1 hour for 6 hours post-challenge while patients are being observed in the observation room, and then every 2 hours up to 18 hours after leaving the clinical unit, while they are home, except for the time that they are sleeping. Further details are provided in the study manual.
7. PNIF is assessed prior to Cat Allergen Challenge, approximately at the time of the EAR, and approximately 6 hours post-challenge while patients are being observed in the observation room. Further details are provided in the study manual.
8. Titrated SPT with Serial Allergen Titration with cat allergen will be performed at screening visit 3, days 29, 85, and 113. On days when an allergen challenge is performed, the test will be performed prior to allergen challenge.
9. FeNO is assessed during screening, Visit 4 and then 24 hours after EEU exposure at day 30 and day 86.
10. All safety assessments performed at screening have to be normal and checked against the inclusion/exclusion criteria prior to REGN1908-1909 administration on day 1 (baseline).
11. On day 1, vital signs are taken prior to PK draw, prior to REGN1908-1909 administration, and at 2 hours (± 10 min) after completion of the injection.
12. Vital signs are taken prior to entry into the EEU, at exit from the EEU, and prior to leaving the clinical trial unit, and any additional times as needed.
13. Telephone call to collect AEs and concomitant medications, including any medications used from the rescue treatment kit, up to 24 hours after the EEU exposure.
14. Total blood draw at any visit will never exceed 60 mL. Blood volumes are never to exceed 350 mL in 12 weeks.
15. Samples are collected prior to administration of REGN1908-1909.
16. On day 1, urine pregnancy test is completed prior to administration of REGN1908-1909 in women of childbearing potential. Postmenopausal women do not need urine pregnancy testing.
17. Total IgE and allergen-specific serum IgE levels (Fel d 2, Fel d 4, Fel d 7).
18. Genomic analysis is mandatory for all patients enrolling in the study. One DNA sample is to be collected on day 1/randomization, but if this sample collection was omitted at baseline, it can be collected at any subsequent visit. [REDACTED]
19. PK samples are drawn at any time in the outpatient visit day from day 8 through day 113 (end of study) visit.
20. After exiting the EEU, patients are monitored outside the EEU in an observation room for approximately 6 hours.

21. Patients will be observed for 6 hours in the observation room after receiving a single dose of REGN1908-1909 or placebo.
22. Blood draws should be performed before the EEU exposure
23. Cat EEU visit 3 and visit 6 must be spaced at least 3 weeks apart
24. Assessments and procedures at the unscheduled visit(s) are to be performed at the discretion of the principle investigator.
25. Screening visits 1 and 2 may be combined into 1 visit if the patient has a historical, positive cat SPT or cat IgE that was completed in the last 12 months.
26. Nasal brushing samples will be collected from the patients before and after Cat Allergen Challenge in the EEU on the day of the screening challenge (visit 3) and day 29 (visit 7). Before the challenge in the EEU, a baseline nasal brushing will be performed in 1 nare and the samples will be processed. Six hours from the start of the EEU challenge, a nasal brushing will be performed in the contralateral nare.
27. Physical examination will be performed prior to entering the EEU and approximately 6 hours after the exit or before leaving the observation room, whichever is later.
28. FSH test to be performed in postmenopausal women only, if postmenopausal status in a woman is in question.

ACT: asthma control test; EEU: environmental exposure unit; PBMC: peripheral blood mononuclear cell; R: randomization; V: visit

